9.1.3. Serious Adverse Events

A SAE is defined in the protocol as any event that: results in death, is immediately life threatening, requires inpatient hospitalization or prolongation of existing hospitalization, results in persistent or significant disability/incapacity, or is a congenital anomaly/birth defect. Important medical events that may not result in death, be life-threatening, or require hospitalization may be considered SAEs when, based upon medical judgment, they may jeopardize the patient and may require medical or surgical intervention to prevent one of the outcomes listed above. A summary table will be presented, together with a further summary table by CTCAE grade.

9.1.4. Relationship of Adverse Events to Study Treatment

The investigator will provide an assessment of the relationship of the event to each of balixafortide and eribulin. The possible relationships are 'related', and 'unrelated'.

Treatment-emergent AEs with a missing relationship will be summarized in tables as 'Related' but will be presented in the data listing with a missing relationship.

A summary table of related TEAEs will be presented, together with a further summary table by CTCAE grade.

9.1.5. Adverse Events Leading to Study Treatment Discontinuation

Following the AE, the investigator will record the action taken with each of the study treatments. If at least one of the drugs has an action taken equal to 'Drug Withdrawn', then the AE will be considered as leading to study treatment discontinuation. The summary table will present overall covering all treatment discontinuations, and separately for each of balixafortide and eribulin where Action Taken with respective treatment is 'Drug Withdrawn'. A summary table by CTCAE grade will also be presented.

9.1.6. Deaths

An AE is leading to death if the outcome is "Death Related to Adverse Event". All deaths and primary reason for patient death will be summarized by treatment arm; deaths within 30 days of the last dose of randomized treatment trial drug will be included. Additionally, deaths related to study treatment will be summarized by treatment arm.

9.1.7. Subgroup Evaluation of Adverse Events

AEs will be also summarized for the following subgroups:

- Patient age (<65yr vs ≥ 65 yr)
- Bone metastases at baseline (Yes vs No)
- Liver metastases at baseline (Yes vs No)

9.1.8. Adverse Events of Special and Adverse Events of Particular Interest

Adverse Events of Special Interest (AESI) and Adverse Events of Particular Interest (AEPI) will be identified by the investigator and specified in the eCRF.

The list of AESI is: Hypersensitivity or IRRs (serious), Neutropenia (serious), Neutropenic infections, Febrile neutropenia, Renal impairment.

The list of AEPI is: Thrombocytopenia, Peripheral neuropathy, Hepatic impairment, QTc prolongation, Hypersensitivity/IRRs, Neutropenia (serious), Neutropenic infections, Febrile neutropenia and Renal impairment.

The number and percent of patients reporting an AESI or an AEPI will be summarized by treatment arm, MedDRA SOC and Preferred term. All AESI categories will be summarized, while only the following categories will be summarized for AEPI: Hypersensitivity/IRRs, Thrombocytopenia, QTc prolongation, Peripheral neuropathy and Hepatic impairment.

Number of patients reporting at least one event of Hypersensitivity/IRR, Neutropenia (serious) or Febrile neutropenia will also be summarized by maximum severity (Grade 1 to 5) and treatment arm.

The number of patients reporting Neutropenic infections will be summarized by treatment arm and maximum severity (Grade 1 to 5). This table will only be populated when at minimum 4 patients reported at least 1 event of Neutropenic infection and the number of such patients is more than 1% of the Safety population.

The number of Colony Stimulating Factor (CSP) medications will be summarized for all patients experiencing Neutropenia events.

The number of Hypersensitivity/IRRs and Neutropenia (serious) will be summarized by cycle, day of onset, in total and split by treatment arm. The number of all Hypersensitivity/IRR will also be summarized in terms of the event intensity allowing for multiple reactions within a patient total; the latter will be achieved by means of a Negative Binomial analysis with a fixed effect term for randomized treatment and time exposed to randomized treatment as the offset. The rate ratio and the corresponding 95% confidence interval will be obtained based on the Wald approach using the log as link function.

Neutropenia (serious) and Febrile neutropenia events will be listed reporting the cycle and day of onset and the duration of the event. The time spent experiencing Neutropenia (serious) and Febrile neutropenia will be summarized by treatment group and severity using the Probability of Being in Event Function, as described by Begg and Larsson (1982).

Separate Kaplan-Meier analysis will be conducted to describe the time to onset of the AESI and AEPI for both treatment arms. Time to onset (months) is defined and calculated as (the earliest date of event onset-date of first dose + 1)/30.4375. Patients who did not develop the event will be censored at their date of death, last trial visit, or the start date of new anti-cancer therapy,

whichever is earlier. Median time to onset and its 95% CI will be estimated for both treatment arms. If the median time to event cannot be estimated due to lack of events, the 25th percentile and its 95% CI will be reported.

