9. ASSESSMENT OF SAFETY

9.1 Safety Assessments

Safety assessments will consist of monitoring all AEs, including SAEs (Section 9.2), regular monitoring of hematology, serum chemistry (Section 9.9), renal function, liver function, ECGs

Protocol No.: POL6326-009

Version 3.0

(Section 9.8), physical examinations (Section 9.6), vital signs (Section 9.7), and ECOG performance status (Section 9.6).

Comprehensive assessment of any apparent AE experienced by the patient will be performed throughout the course of the study, from the time that the patient receives the first dose of study medication until 30 days after the last study drug administration; SAEs will be recorded from the date that the ICF is signed.

Study site personnel will report any AE, whether observed by the Investigator or reported by the patient.

AE assessment will include type, incidence, severity (graded by National Cancer Institute Common Terminology Criteria for Adverse Events [NCI CTCAE] version 5.0, see Section 9.2.3, Severity Assessment), timing, seriousness, and relatedness.

Adverse Events of Particular Interest and Adverse Events of Special Interest

AEPIs include all events of special interest and additionally, all events for which a separate analysis will be performed (Table 9).

AEPIs are based on the emerging AE profile of balixafortide or on the established risks associated with eribulin.

All grade events of thrombocytopenia, peripheral neuropathy, hepatic impairment and QTc interval prolongation have been identified as AEPIs.

Serious events of IRRs, neutropenia and infection, and all cases of renal impairment will be considered AESIs, as well as being AEPIs.

AESIs are to be reported by the Investigator to the Sponsor within **24 hours** of learning of the event.

AESIs must be reported using the same form as for SAEs and notified to the Sponsor within **24 hours** of the Investigator becoming aware of the event, irrespective of causality with the study drug.

Protocol No.: POL6326-009

Version 3.0

Table 9 AEs of Particular Interest and AEs of Special Interest

Adverse Events of Particular Interest	Definition
Thrombocytopenia	Defined using SMQ "Haematopoietic Thrombocytopenia narrow". SMQ code 20000031
Peripheral neuropathy	Defined using SMQ "Peripheral neuropathy narrow" SMQ code 20000034
Hepatic impairment	Defined using SMQ "Liver related investigations, signs and symptoms (SMQ) narrow" SMQ code 20000008

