QTc prolongation	Defined using SMQ "Torsade de pointes/QT prolongation "SMQ code 20000001
Hypersensitivity/IRRs	IRRs are defined as AEs that are deemed related to any study treatment by the Investigator, which occurred during infusion or within 24 hours from the end of infusion. Note: IRRs encompass AEs reported as the MedDRA PT "Infusion related reaction" (within the SOC "Injury, Poisoning and Procedural Complications") together with reported signs and symptoms of IRRs
Neutropenia (serious)	Based on reported AEs rather than laboratory values. Defined using SMQ "Haematopoietic Cytopenia" SMQ code 20000027
Neutropenic infections	Defined by PT neutropenic infection
Febrile neutropenia	Defined by the PT febrile neutropenia
Renal impairment	Defined using SMQ "Acute renal failure" SMQ code 20000003
Adverse Event of Special Interest	Definition
Hypersensitivity/IRRs (serious)	IRRs are defined as AEs that are deemed related to any study treatment by the Investigator, which occurred during infusion or within 24 hours from the end of infusion. Note: IRRs encompass AEs reported as the MedDRA PT "Infusion related reaction" (within the SOC "Injury, Poisoning and Procedural Complications") together with reported signs and symptoms of IRRs
Neutropenia (serious)	Based on reported AEs rather than laboratory values
Neutropenic infections	Defined by PT neutropenic infection
Febrile neutropenia	Defined by the PT febrile neutropenia
Renal impairment	Defined using SMQ "Acute renal failure" SMQ code 20000003

AE: adverse event; IRR: infusion-related reaction; MedDRA: Medical Dictionary for Regulatory Activities; PT: preferred term; QTc: corrected QT interval; SMQ: Standardized MedDRA query; SOC: system order class.

Baseline tumor-related signs and symptoms will be recorded at the Cycle 1, Day 1 visit and then reported as AEs (Section 9.2.5) during the study if they worsen in severity or increase in frequency.

Protocol No.: POL6326-009

Version 3.0

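### SAP 9.1.8 has open-label investigators identify AESIs and AEPIs in the eCRF, although protocol Table 9 defines eight of the nine AEPI categories on coded terms; SAP section 12 does not record the difference

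*SAP*

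**What the plan says.** Protocol section 9.1 links Table 9 to analysis and not only to site reporting: "AEPIs include all events of special interest and additionally, all events for which a separate analysis will be performed (Table 9"). Protocol section 12.4.1 sends the reader back to section 9.1 for the AESIs. Table 9 then gives each category a definition, for example:

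- SMQ with its scope stated: "Defined using SMQ 'Peripheral neuropathy narrow' SMQ code 20000034"
- SMQ with no scope stated: "Defined using SMQ 'Acute renal failure' SMQ code 20000003"
- single preferred term: "Defined by the PT febrile neutropenia"
- serious neutropenia, in the AEPI half only: "Defined using SMQ 'Haematopoietic Cytopenia' SMQ code 20000027"
- IRR, by investigator judgement and timing: "AEs that are deemed related to any study treatment by the Investigator, which occurred during infusion or within 24 hours" from the end of infusion.

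SAP section 9.1.8 keeps the same nine category names but states another rule: "Adverse Events of Special Interest (AESI) and Adverse Events of Particular Interest (AEPI) will be identified by the investigator and specified in the eCRF". It names no SMQ, gives no defining preferred term and does not cite Table 9. It tabulates every AESI category, while "only the following categories will be summarized for AEPI: Hypersensitivity/IRRs, Thrombocytopenia, QTc prolongation, Peripheral neuropathy and Hepatic impairment". Serious neutropenia is therefore tabulated as an AESI, and the AESI row of Table 9 is the one that omits its SMQ.

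SAP section 12 sets out to list changes from the protocol as well as from SAP version 1.4.

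**The concern.** The trial is open-label (SAP section 4.2), so whoever sets the eCRF flag may know the treatment arm. If the flag defines the category, site judgement decides who enters the by-arm AESI and AEPI counts. In the time-to-onset analysis, a patient who is not flagged is censored as event-free. Even without bias, flagging site by site groups events less reproducibly than a fixed term list does. AE type, frequency and severity, AESIs included, is a named secondary safety endpoint (protocol section 4.4.3; SAP section 3.2.4), so two different rules for who counts should not stand side by side.

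**Working it through.** No formula or stated figure is involved. The check is a count of definitions and of the outputs that depend on them.

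**Definitions** (protocol Table 9) against SAP 9.1.8 and the outputs that do not use the flag (SAP 9.1.1, 9.2, 9.5):

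| Category | AEPI half | AESI half | Tabulated in SAP 9.1.8 as | Flag-free outputs |
|---|---|---|---|---|
| Thrombocytopenia | SMQ, narrow | – | AEPI | preferred-term rows; platelets |
| Peripheral neuropathy | SMQ, narrow | – | AEPI | preferred-term rows only |
| Hepatic impairment | SMQ, narrow | – | AEPI | preferred-term rows; liver tests |
| QTc prolongation | SMQ, no scope | – | AEPI | preferred-term rows; QTcF |
| Renal impairment | SMQ, no scope | same SMQ | AESI | preferred-term rows; creatinine |
| Serious neutropenia | SMQ, no scope | no SMQ | AESI | preferred-term rows for serious TEAEs; neutrophils |
| Neutropenic infection | one preferred term | same | AESI | its own preferred-term row |
| Febrile neutropenia | one preferred term | same | AESI | its own preferred-term row |
| Hypersensitivity/IRR | investigator relatedness, 24 hours | same, serious only | both | not a coded definition |

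- AEPI half: 6 SMQ + 2 preferred term = 8 of 9 coded; 9 − 8 = 1 rests on investigator judgement.
- AESI half: 3 of 5 coded (neutropenic infection, febrile neutropenia, renal impairment).
- SAP 9.1.8: 0 of 9 with a coded definition.

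**Declaration.** SAP section 12 has 11 bullets. One mentions AESIs and AEPIs; it concerns which categories are tabulated and by what breakdown. None concerns how events are identified.

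**What depends on the flag, among the eight coded categories:**

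- Incidence: 4 as AEPI + 4 as AESI = 8. The two single-preferred-term categories can be read directly from the general TEAE tables, which leaves 8 − 2 = 6 SMQ categories whose grouped count appears nowhere else. Adding preferred-term rows does not recover it, because one patient may appear in several rows.
- Kaplan-Meier time to onset: all 8, with no flag-free equivalent.
- Time in event: 2 (serious neutropenia, febrile neutropenia).
- Counts by cycle and day of onset: 1 (serious neutropenia); the other category so treated is IRR.
- Negative binomial rate model: 0; it covers IRR only.
- Severity: unclear. SAP 9.1.8 gives maximum severity for four categories (IRR, serious neutropenia, febrile neutropenia and, conditionally, neutropenic infection). The section 12 bullet says that all AESIs and the non-overlapping AEPIs are summarized by toxicity grade. The two places disagree.

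**The case against.** The strongest reply is that nothing has been shown to change. SAP 9.1.8 uses the protocol's nine categories and states no rival term list, and the eCRF field may have been built on Table 9. The protocol already has investigators notify AESIs within 24 hours. Protocol section 12.4.1 prescribes no SMQ derivation and leaves table content to the SAP. Preferred-term tables by arm and grade, AE listings, the programmed liver-injury criteria and the QTcF categories all work without the flag.

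Much of this stands, and it sets the limits:

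- A reader might infer that the SAP has discarded Table 9. The documents do not show that; they show a stated rule that does not refer to it, with the eCRF instructions unavailable.
- A reader might infer that leaving the rule out of section 12 breaches the protocol. It does not: protocol section 12.1 lets changes to non-confirmatory analyses be listed in the CSR, and section 12.5 accepts an amendment, the final SAP or the trial report. SAP version 1.4 is not available for comparison either.
- A reader might infer that the safety comparison is biased in a known direction. Nothing in the documents supports a direction or a size.

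The 24-hour duty does not settle the matter. It governs notification of AESIs, not the analysis definition, and it does not reach the four AEPI-only categories (thrombocytopenia, peripheral neuropathy, hepatic impairment, QTc prolongation).

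**Conclusion.** The point holds as an unreconciled difference between two rules for the same categories. The protocol offers coded definitions for eight of nine AEPI rows; the SAP names investigator identification for all nine and does not connect the two. The weight is low to moderate. What is at stake is mainly the grouped by-arm patient count in the six SMQ categories, time to onset in all categories, and time in event for serious and febrile neutropenia. Peripheral neuropathy is the most exposed, having no laboratory or ECG counterpart.

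The outputs are descriptive and outside Type I error control. The conclusion assumes that the eCRF flag, as SAP 9.1.8 says, is what selects events for these outputs. If the field already follows Table 9, a sentence saying so would settle most of the matter. Coded derivation would reduce open-label influence but not remove it, because reporting an AE at all is the investigator's decision.

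**What to change.** In SAP 9.1.8:

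- Derive thrombocytopenia, peripheral neuropathy, hepatic impairment, QTc prolongation, renal impairment, febrile neutropenia and neutropenic infection programmatically from the MedDRA-coded AEs, using Table 9. State the SMQ scope for QTc prolongation and renal impairment, where Table 9 gives none.
- For serious neutropenia, first reconcile the AEPI and AESI rows and restrict the list to neutropenia terms: the cited SMQ is titled Haematopoietic Cytopenia and, on its title, could bring in other cytopenias. Then derive it with the seriousness condition.
- Reconcile the neutropenic-infection definition. Table 9 uses one preferred term with no seriousness condition, the text of protocol section 9.1 speaks of serious infection, and section 2.6 of infections that accompany neutropenia.
- Keep investigator identification for IRR, citing Table 9's relatedness and 24-hour definition. A purely timing-based rule is not advised: AE start times may be missing, there is no list of signs and symptoms, and the arms have six versus two infusion days per cycle.
- Keep the eCRF flag for expedited reporting.
- Align 9.1.8 and section 12 on which categories are summarized by grade, and record the identification rule in section 12.

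The cost is SAP wording, the definitional decisions above and standard SMQ and preferred-term programming. AEs are already to be coded in MedDRA (SAP section 9.1), so no new data are needed.

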5.4 Patient Restrictions

5.4.1 Prior or Concomitant Medication

Patients must be instructed not to take any additional medications (over-the-counter or other products) during the study without prior consultation with the Investigator. Any medications, including herbal supplements, vitamins, or treatment taken by the patient, from 28 days prior to the start of study medication and up to 30 days (and no later than 37 days) following the last dose of study drug (as described in Section 7.7) and the reason for their administration must be recorded on the patient's source data and eCRF.

Routine postoperative care, such as dressing changes, suture removal, drain removal, does not need to be recorded. Anesthetics used for any surgical procedures performed during the patient's participation in the study can be recorded as "unspecified anesthesia" on the concomitant treatment records; it is not necessary to list the specific anesthetics. Palliative and supportive care for cancer-related symptoms can be used and must be recorded in the patient's source data and eCRF.

Protocol No.: POL6326-009

Version 3.0

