5.4.2 Permitted Medications

The following are permitted throughout the duration of the treatment:

• Standard therapies for pre-existing medical conditions, medical and/or surgical complications, and palliation may be used during this study. Any medication intended solely for supportive care (e.g., analgesics, antidiarrheals, antidepressants) may also be used at the Investigator's discretion. All medications must be recorded in the patient's source data and eCRF.

- Antihistamines (H₁ receptor antagonists) and corticosteroids can be used to manage IRRs Section 9.2.6.3). At the discretion of the treating physician, H₁ receptor antagonists may be used as premedication for the prevention of IRRs.
- Hematopoietic growth factors (e.g., granulocyte colony stimulating factor [G-CSF], granulocyte macrophage colony stimulating factor [GM-CSF]): Receipt of CSFs within 14 days prior to study Day 1 (Cycle 1) are not permitted (Section 5.2). However, after study Day 1 (Cycle 1), this study requires adherence to the ASCO guidelines for minimizing the incidence of febrile neutropenia, including the recommended prophylactic use of CSFs, where appropriate at the discretion of the Investigator (Appendix 7 ASCO Guidance on the Use of CSFs) (54). Risk factors for febrile neutropenia in addition to those posed by eribulin and advanced BC are shown in Table 10.
- **Erythropoietin** may be used at the Investigator's discretion for the supportive treatment of anemia.
- **Bisphosphonates** may be continued for the treatment of osteoporosis or management of existing bone metastases for patients who have been receiving them at a stable dose for at least 4 weeks prior to randomization (Section 5.1). If the dose is increased or therapy is initiated during the study, the reason must be documented in the patient source documentation and disease progression according to RECIST v1.1 must be ruled out.
- Palliative radiotherapy is permitted if done solely for bone pain relief. If palliative radiotherapy is initiated after start of study medication, the reason for its use must be clearly documented and disease progression according to RECIST v1.1 must be ruled out.

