12.2.6 Treatments and Medication

12.2.6.1 Prior and Concomitant Medication

Prior and concomitant medications will be recorded on the source data and eCRF and coded to ATC code and preferred drug name using the latest version of WHO-DDE. Concomitant medications will be tabulated for the Safety Population by WHO-DDE ATC.

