7.1. Prior and Concomitant Medications

Prior and concomitant medications will be recorded on the eCRF and coded to as per ATC and preferred drug name using the prevailing version of the WHO-DDE dictionary. The summary tables will be ordered by descending incidence of ATC class and by descending incidence of preferred drug name within each ATC class for all patients.

Concomitant medications are defined as medications with a start date on or after the date of the first dose in Cycle 1 up to 30 days following the last dose of study treatment in the study; it will also include medications initiated prior to the date of the first dose of study treatment and continued during treatment.

Concomitant medications will be summarized by treatment for the Safety set by WHO-DDE ATC classification and preferred term. If the ATC level-2 classification is missing, the next nonmissing lower level of classification will be used (level 1). If a patient reports the same medication multiple times, then that medication will be counted only once. If a patient reports multiple medications within the same ATC level-2 classification, then the frequency for that ATC level-2 classification will be incremented by only one. Percentages will be calculated using the total number of patients in the Safety set.

Prior medications are defined as medications taken from 28 days prior to the first dose of study treatment in Cycle 1. Prior medications will be summarized similarly to concomitant medications for the ITT (3rd line+) set. Percentages will be calculated using the total number of patients in the ITT (3rd line+) set.

Prior and concomitant medications will be presented in a data listing.

Post anti-cancer therapies (therapies applied after study treatment discontinuation for subjects that are continuing in the study for the FU phase) as reported in Post Anti-Cancer Therapy eCRF page will be summarized for the corresponding ITT (3rd line+) set, using the WHO-DDE and ATC level-4 classifications and preferred term. The number and percent of patients who took at least one post anti-cancer therapy will be calculated and presented by treatment arm, ATC level-4 classifications, and preferred term.

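### The one dedicated CSF summary covers only patients with neutropenia events, and the general medication table gives ever-use by arm without reason or timing, so neither separates prophylaxis from treatment

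*SAP*

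**What the plan says.** **Dedicated summary.** SAP 9.1.8 states: "The number of Colony Stimulating Factor (CSP) medications will be summarized for all patients experiencing Neutropenia events". (CSP is the SAP's own abbreviation for colony stimulating factor.) The sentence counts medications and does not mention treatment arm, reason or timing. It also does not say whether it means serious neutropenia only or any neutropenia event.

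**General medication table.** SAP 7.1 states: "Concomitant medications will be summarized by treatment for the Safety set by WHO-DDE ATC classification and preferred term". The denominator is everyone treated: "Percentages will be calculated using the total number of patients in the Safety set". The counting rule is: "If a patient reports the same medication multiple times, then that medication will be counted only once". A listing is also planned: "Prior and concomitant medications will be presented in a data listing". Protocol 12.2.6.1 plans the same kind of table: "Concomitant medications will be tabulated for the Safety Population by WHO-DDE ATC".

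**CSF policy.** From Cycle 1, Protocol 5.4.2 requires adherence to a guideline for limiting febrile neutropenia, "including the recommended prophylactic use of CSFs, where appropriate at the discretion of the Investigator". Protocol 6.1.2.1 and 9.2.6.4 repeat this.

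**Data collected.** For every medication, Protocol 5.4.1 says that "the reason for their administration must be recorded on the patient's source data and eCRF".

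**The concern.** Three of the five AESI categories in SAP 9.1.8 are serious neutropenia, neutropenic infection and febrile neutropenia. Comparing them between arms is part of judging the safety of adding balixafortide. Investigators know the arm and decide where prophylaxis is appropriate, so CSF use may differ between arms.

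Unequal use could arise in two ways that mean opposite things. More prophylaxis in one arm lowers that arm's observed neutropenia. More neutropenia in one arm leads to more CSF given as treatment. To interpret the event rates, a reader needs to know which happened. A summary restricted to patients who had an event cannot show it, because successful prophylaxis removes a patient from the summary.

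The effect reaches beyond the AESI table. Under Protocol 6.1.2 and 6.1.2.1, low neutrophil counts lead to eribulin delays and reductions, and SAP 9.1.1 summarises events leading to the first eribulin reduction by arm.

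**Working it through.** The plan states no figure for this point, so there is nothing to reproduce. The check has two parts.

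**1. What each planned output can show**

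| | SAP 9.1.8 CSF summary | SAP 7.1 medication table |
|---|---|---|
| Patients | Those with neutropenia events | Whole Safety set |
| By arm | Not stated | Yes |
| Patients whose prophylaxis worked | Omitted | Counted |
| Prophylaxis separated from treatment | No | No |
| Timing or cycle | No | No |
| One row for any CSF | Not stated | Not stated |

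On the last row, the exclusion criteria in Protocol 5.2 name three agents. A patient given two of them appears under two preferred terms, so those rows cannot be added to give CSF users. No neutropenia analysis in SAP 9.1.8 refers to CSF use outside the event-restricted summary.

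**2. Illustration of masking**

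Inputs:
- Febrile neutropenia on eribulin is 5% (Protocol 9.2.6.4), taken here as the risk without CSF. The protocol does not state the CSF use behind that figure.
- Combination risk without CSF is 5% × 1.5 = 7.5% (ratio assumed).
- Relative risk under prophylaxis is r = 0.5 (assumed).
- Share given prophylaxis is 20% on eribulin and 50%, 60% or 80% on the combination (assumed).
- 192 patients per arm (Protocol 3.3).

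Formula: observed risk = p × (1 − c × (1 − r)), where p is the risk without CSF and c the share given prophylaxis.

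- Eribulin: 5% × (1 − 0.2 × 0.5) = 4.5%.
- Combination, c = 50%: 7.5% × 0.75 = 5.63%; ratio 1.25.
- Combination, c = 60%: 7.5% × 0.70 = 5.25%; ratio 1.17.
- Combination, c = 80%: 7.5% × 0.60 = 4.5%; ratio 1.00.
- Equal 20% use in both arms: the ratio stays at 1.50.

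With use at 60% against 20%, the ratio is 1.01, 1.17 or 1.31 for r = 0.3, 0.5 or 0.7. The 5% cancels from every ratio, so the ratios rest wholly on assumed inputs.

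Patients missed by a summary limited to febrile neutropenia cases (r = 0.5, 60% against 20%):
- Eribulin: 192 × 0.2 = 38.4 users; 38.4 × (1 − 0.025) = 37.4 have no event, about 37 of 38.
- Combination: 192 × 0.6 = 115.2 users; 115.2 × (1 − 0.0375) = 110.9 have no event, about 111 of 115.

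The share of cases who had prophylaxis is c × r / (c × r + 1 − c): 0.1/0.9 = 11% and 0.3/0.7 = 43%, against true use of 20% and 60%. CSF given to treat the event would be added on top. If the SAP means neutropenia of any grade, fewer prophylaxis users would be omitted. All of these users would still be counted by arm in the SAP 7.1 table.

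**The case against.** A reader might infer that CSF use is reported only for patients with neutropenia, so that unequal use would stay hidden. The documents do not support that. SAP 7.1 covers the whole Safety set by arm, and the assumed imbalance of 50–80% against 20% would be plain there. This part of the objection stands and limits the point to reason and timing.

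A reader might also take 1.25, 1.17 and 1.00 as a bias that a better table would remove. They are not: no table changes an event rate. They show only why the reader needs to know how CSF was used.

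Three further arguments favour the plan as written:

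- **The same guideline applies to both arms**, so a comparison under that supportive care is legitimate, and the 9.1.8 sentence may be meant only to describe how neutropenia was managed. This is fair. But the arms can still differ in discretionary use, and no other planned table describes prophylaxis.
- **The listings hold the answer.** Medications are listed, and serious and febrile neutropenia events are listed with cycle, day of onset and duration. That is true patient by patient, but listings give no summary by arm.
- **Neutrophil counts are summarised by arm, cycle and day.** CSF alters those counts too. Scheduled samples fall on Days 1 and 8 or Days 2 and 9 (SAP 9.2), while Protocol 9.2.6.4 gives a mean time to nadir of 13 days. Protocol 2.2 also describes white cell release by balixafortide itself.

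**Conclusion.** The point holds as a reporting gap in a descriptive safety analysis. The dedicated CSF summary is conditioned on a post-randomisation outcome that CSF changes. The general table corrects the population but gives only ever-use. Neither lets a reader say whether higher CSF use in one arm is a cause of its observed neutropenia rate or a consequence of it.

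The documents give no CSF use rates and no CSF effect, so the size cannot be estimated from them. Under the stated assumptions, a true ratio of 1.5 could appear as anything from 1.25 to 1.00. No efficacy endpoint, alpha allocation or sample size is affected. The change is worth making because the neutropenia comparison bears on benefit and risk, and the data are already collected.

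**What to change.** Replace the CSF sentence in SAP 9.1.8 with text to this effect:

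> Use of any CSF will be summarised by treatment arm in the Safety set and the Safety set (3rd line+), as the number and percentage of patients and the number of cycles with CSF. Use will be divided into prophylaxis and treatment by the reason for administration recorded in the eCRF, supported by CSF start date relative to onset of the first neutropenia event. The summary will be shown beside the rates of serious and febrile neutropenia by arm. It is descriptive, because CSF use is post-randomisation.

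The recorded reason should lead and the date should support it. Under Protocol 9.2.1, a low count need not be reported as an AE, so a date-only rule would label CSF given for such a count as prophylaxis. SAP 4.4 also sets a missing start day for a medication to the first of the month, which can place CSF before an event that it was given to treat. The SAP should say how imputed dates and missing or unclear reasons are classified.

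A table of neutropenia by prior CSF use is confounded by indication. It should be optional and labelled as such.

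The cost is one more descriptive table, some coding of the recorded reasons, and no new data collection.
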